#### **13.4 Sample Size/Accrual Rate**

We expect that at most 10% will potentially drop out prior to administration of the 2nd vaccination, which translates to a total maximum sample size of  $22+2=24$  in each arm for a total of 48 patients. With an anticipated accrual rate of about 3 patients per month, we expect that this trial will be fully accrued in at most 16 months.

#### **13.5 Analysis of Secondary Endpoints**

In addition to evaluating the proportion of patients who have a vaccine-related antibody response to PCV13, we will also evaluate the seroconversion rates and antibody titre levels for each of the serotypes of the 13-valent pneumococcal vaccine. These markers will be summarized using descriptive statistics by treatment arm. We will graphically evaluate changes in these serotype-specific markers between the two arms, and we will also use the nonparametric Mann-Whitney rank sum test to compare the geometric mean concentrations.

Secondary endpoints will also include the CR rate following 2 years of lenalidomide treatment. Assuming that the number of CRs is binomially distributed, then we will also generate corresponding 95% confidence intervals for the CR rate estimate. If there is also a significant difference between the arms in terms of the vaccine response to PCV13, then we will also compare the CR rates between the two arms in an exploratory manner, although we will only be able to detect a large differential in CR rates (10% vs. 40%) with at least 80% power and a Type I error rate of 10%. In addition, we will evaluate time to event outcomes such as time to first treatment (TFT) and overall survival (OS). TFT will be defined as the time from study entry to first therapy for progressive CLL as defined by IWCLL 2008 criteria. To evaluate this endpoint, patients will be followed even after discontinuing therapy, where we will document date of subsequent treatment and/or progressive disease. Survival will also be evaluated, although we do not expect

many events in this early stage, asymptomatic group of patients. Time to event outcomes will be summarized and explored between treatment arms using Kaplan-Meier methods. Formal comparison of these endpoints between the two arms will not be done due to lack of statistical power to do so. In a very exploratory manner, we will also assess time to treatment in relation to the results reported by Shanafelt et al (2009); in an exploratory manner, we will utilize their prognostic scoring to identify an expected versus observed time to treatment.[64-65]

In each arm, we will evaluate the overall and complete response rates after two years, the proportion of patients in each arm who are progression-free at 2 years, and safety and tolerability of each regimen. Adverse events will be summarized by and across treatment arms, where we will summarize the type, severity, and perceived attribution to study treatment according to NCI's CTCAE (version 5). The rates of severe (grade 3+) toxicity (at least possibly related to treatment) and non-hematologic toxicity will be summarized; assuming the incidence of severe toxicity is binomially distributed, 95% confidence intervals will be calculated. The maximum grade for each type of toxicity will be recorded for each patient, and frequency tables will be reviewed to determine the toxicity patterns. In addition, we will assess time to treatment failure, defined as the time from study entry to discontinuation of treatment; we will also summarize reasons patients discontinue study treatment.

Descriptive statistics (i.e. means, standard deviations, 95% confidence intervals for continuous variables and frequencies for discrete data) will be computed for all correlative laboratory parameters. Given the small sample size in this phase II trial, a total of 44 patients may limit our ability to perform inferential tests. Still, we will graphically evaluate these PK and PD markers within and across arms to assess potential patterns and relationships. Where model assumptions are met, we will also utilize repeated measures models (linear or nonlinear mixed models, generalized estimating equation models) to explore relationships with the various markers and clinical outcomes of interest.

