### **9.1.1 Collection of Specimens**

In Arm A (Concurrent), serum antibody levels specific to each of 7 pneumococcal antigens contained in the PCV13 vaccine will be assessed at Cycle 1 Day 1 (baseline), 2 months following initiation of lenalidomide therapy (Cycle 3 Day 1), 2 months after initial vaccination (Cycle 5 Day 1) and 1 month after second vaccination (Cycle 6 Day 1) and every 6 months thereafter for patients remaining in follow-up. For those in Arm B, titers will be assessed at Cycle 1 Day 1(baseline), 2 months after initial vaccination (Cycle 3 Day 1), 1 month after second vaccination (Cycle 4 Day 1), and every 6 months thereafter.

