### 13.3 Study Design

In this trial, patients will be randomized in a 1:1 allocation to receive lenalidomide with PCV13 up front concurrently (Arm A) vs. PCV13 up front and then subsequent administration of lenalidomide (Arm B). In this study we will compare the proportion of patients in each arm who achieve a significant antibody response as defined above. While it is not typical to employ a direct comparison of primary endpoints in the phase II setting, we believe that a randomized phase II design will better control for cohort and sampling variability necessary to assess the primary endpoint. In addition, in a secondary manner, we will also evaluate the clinical efficacy of treatment with lenalidomide in these patients vaccinated with PCV13, where clinical efficacy will be primarily determined through the proportion of patients who achieve a CR within two years (see Analysis Plan for more details).

Randomization will be stratified on exposure to pneumococcal vaccination in the previous 5 years. Those patients who have previously received a polysaccharide pneumococcal vaccine will not be excluded. If a patient drops out of the study prior to administration of a 2nd (booster) pneumococcal vaccination, they will not be considered evaluable for the primary endpoint and will be replaced on the study. However, the patient will be included in analyses of efficacy and tolerability as appropriate.

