Assuming that vaccine success in each arm is binomially distributed, we will use a two-sided chi-square test to compare the difference in proportions. We will constrain the Type I error rate in the comparison of vaccine response rates to 0.10. Using a two-sided test, we will have at least 90% power to detect a difference of 0.40 between the two rates (0.20 vs. 0.60) with a total of 44 evaluable patients (22 in each arm). Comparing these two vaccine success rates, if  $p_A \neq p_B$  and the resulting p-value  $< 0.10$ , we will consider the arm with the higher antibody response rate to have a significantly higher rate of vaccine success than the other arm. This design also allows for an interim analysis to be conducted after 11 patients have been accrued to each treatment arm (i.e. 50% of total planned accrual). Under a Lan-DeMets alpha spending function to constrain the Type I error rate, we will consider it sufficient evidence that one arm has a significantly higher antibody response rate than the other arm if the observed p-value  $< 0.0056$  (design generated using East version 5.3).

Independent of the comparison of vaccine-related efficacy, we will also formally evaluate

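### The only test named for comparing serotype-specific concentrations between arms is an unadjusted rank-sum test, which yields no geometric mean ratio and leaves the baseline titre and the stratum unused

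*Combined protocol and SAP*

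**What the plan says.** Section 13.5 of the combined protocol and SAP summarises titres descriptively by arm and adds a plot: "We will graphically evaluate changes in these serotype-specific markers between the two arms". It then names one test: "we will also use the nonparametric Mann-Whitney rank sum test to compare the geometric mean concentrations". For that test it gives no time point, covariate, stratum, significance level, effect estimate or confidence interval.

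Three other places bear on this:

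- Section 9.1.1 schedules a titre at Cycle 1 Day 1 in both arms, and one month after the second vaccination (Arm A Cycle 6 Day 1, Arm B Cycle 4 Day 1).
- Section 13.3 stratifies randomisation on pneumococcal vaccination in the previous five years and admits patients who have had a polysaccharide vaccine.
- Section 13.5, in its later paragraph on correlative laboratory parameters, says that where assumptions hold "we will also utilize repeated measures models (linear or nonlinear mixed models, generalized estimating equation models) to explore relationships" between markers and clinical outcomes. It mentions neither a baseline-adjusted contrast between arms nor the titres by name.

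**The concern.** The named quantity and the named test do not match. A rank-sum p-value is the same on raw and log concentrations. It concerns the probability that a patient in one arm has a higher value than a patient in the other. It does not estimate a GMC ratio, and a reader of the results will want that ratio and its interval.

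The test also leaves out two variables that the design itself treats as relevant. The primary endpoint is defined partly as a rise from baseline, and prior vaccination is the stratification factor. With 22 patients per arm, a chance difference in starting titres would pass straight into the comparison. At stake are the interpretability and precision of a secondary result in a small trial.

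**Working it through.** **The plan's own figure.** The 22 per arm comes from the primary comparison of 0.20 with 0.60 at two-sided 0.10. With unpooled variance, 0.40 / √[(0.16 + 0.24)/22] − 1.645 = 2.966 − 1.645 ≈ 1.32, which gives 90.7% power, so the stated 90% reproduces. The exact power of the uncorrected chi-square test is about 88%. No figure is stated for the concentration comparison.

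**Does the rank-sum test compare geometric means?** Under a pure shift on the log scale it is a valid test that the GMC ratio is 1. To see what happens otherwise, two arms of 22 were simulated with equal log means but different shapes (shifted exponential against normal). At a nominal 10% the rank-sum test rejected 13.1% of the time, and a t-test on logs 10.2%.

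**What does baseline adjustment buy?** Inputs from the documents: 22 evaluable patients per arm and 1:1 allocation (Section 13.3), and a Cycle 1 Day 1 titre in both arms (Section 9.1.1). Assumptions, because the documents are silent: the SD of log titre, the true ratio, and the baseline to post-booster correlation ρ, shown from 0 to 0.7. The simulations adjust for baseline only, not for the stratum.

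The variance of the adjusted difference relative to the unadjusted one is about (1 − ρ²) × [1 + 1/(2n − 4)]. With n = 22 the second factor is 1 + 1/40 = 1.025.

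Scenario 1 uses two-sided 5%, SD 0.5 log10 and ratio 2.5, so the effect is log10(2.5)/0.5 = 0.398/0.5 ≈ 0.80 SD. Scenario 2 uses an effect of 0.75 SD and two-sided 10%. That is the level of the primary comparison ("We will constrain the Type I error rate in the comparison of vaccine response rates to 0.10"); none is set for this one. Log titres are normal in both.

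| ρ | Variance factor | Scenario 1: rank-sum | Scenario 1: ANCOVA | Scenario 2: rank-sum | Scenario 2: ANCOVA |
|---|---|---|---|---|---|
| 0 | 1.025 | 71% | 71–72% | 77% | 78% |
| 0.3 | 0.933 | 71% | 76% | 77% | 81% |
| 0.5 | 0.769 | 71% | 83% | 77% | 87% |
| 0.7 | 0.523 | 71% | 94% | 77% | 96% |

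In Scenario 2 the type I error of ANCOVA stayed at its nominal level (0.100 to 0.104). An unadjusted t-test on logs had about 79% power there, so some two points of the difference come from using a parametric test rather than from the baseline.

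**Less favourable data, two-sided 10%, at ρ = 0, 0.3, 0.5 and 0.7:**

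- With 31% of baseline values at an assay floor, the change from rank-sum to ANCOVA is about 0, +3, +8 and +17 points.
- With a responder mixture (20% against 60% responding, responders shifted by 2 SD), it is about −1, +1, +4 and +10 points. At 5% the mixture gives a range of about −1 to +11.

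**Would a rank-sum test on log change do instead?** In Scenario 2 its power is 52%, 64%, 77% and 92% at the same correlations. It does worse than post-booster values alone when ρ is below 0.5, so it is not a safe substitute.

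**The case against.** Several points on the other side are sound.

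- A nonparametric test with 22 per arm is a defensible choice. A reader might infer that the rank-sum test is invalid for GMCs. That goes too far, because under a log-scale shift it does test their equality. What stands is that the plan does not state that condition and promises no estimate.
- A reader might infer that the trial throws the baseline titre away. It does not: the primary endpoint uses it, and changes are plotted. Section 13.5 does not even fix the time point or scale of the test. The omission belongs to this one test as written.
- Titres are themselves listed under correlative studies in Sections 2.5.6 and 9.1. The descriptive confidence intervals and exploratory repeated-measures models could therefore be read as covering them. That is a fair reading, but neither item commits to a baseline-adjusted contrast between arms or to a ratio with an interval.
- A reader might call ANCOVA a free gain in power. The documents give neither the correlation nor the SD. Moreover, the design assumption of 20% against 60% responders suggests mixed distributions, where the gain is small and can be slightly negative. ANCOVA also needs a roughly linear relation on the log scale and a rule for values at the assay limit. A rank-sum test cannot serve as a check on normality.
- Section 9 says the study endpoints have been met and stops research sampling. Replacing a planned test now could look data-driven. This favours adding the ANCOVA and keeping the planned test.

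**Conclusion.** The point holds as a matter of specification and reporting for a secondary comparison. The single named test does not in general compare geometric means, no GMC ratio with a confidence interval is specified, and the test uses neither the baseline titre nor the stratum.

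The case for the estimate and its interval does not depend on the correlation. The case for more power does. Under normal log titres the gain at 5% runs from about nothing at ρ = 0 to about 23 points at ρ = 0.7 (94 − 71). Under a responder mixture it runs from about −1 to +11. Every one of these figures rests on an assumed effect, spread and correlation.

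It would be wrong to infer that the trial's main conclusion is at risk. This comparison carries no stated significance level or decision rule, and neither the primary chi-square test nor the 44 evaluable patients depends on it.

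**What to change.** In Section 13.5, for each measured serotype (Section 9.1.1 specifies seven), add an ANCOVA of log post-booster IgG:

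- Outcome time: Cycle 6 Day 1 in Arm A and Cycle 4 Day 1 in Arm B.
- Terms: arm, log Cycle 1 Day 1 IgG and the randomisation stratum. The Arm A Cycle 3 Day 1 titre should not serve as baseline, because it follows two cycles of lenalidomide.
- Report: the back-transformed GMC ratio with a confidence interval.
- State how values at the assay limit are handled before logs are taken.
- Keep the Mann-Whitney test alongside, at a named time point, and do not describe it as a test of GMCs.
- If titres have already been analysed, label the ANCOVA post hoc.

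The cost is some SAP wording and a short piece of code, with no new patients or samples. The price is reliance on a log-linear model and, if the baseline correlation is near zero, a loss of about 2.5% in variance (the factor 1.025 above).

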### **Arm B: Sequential**

Month 1	Month 2	Month 3	Month 4	Month 5	Month 6	Month 7	Month 8+
V		V					
			L	L	L	L	L

V = PCV13 pneumococcal vaccine administration; L = lenalidomide

Patients will be randomized to receive concurrent lenalidomide and pneumococcal vaccine (Arm A) or sequential pneumococcal vaccine alone followed by lenalidomide (Arm B). Since the primary endpoint is to determine the change in anti-pneumococcal antibody titer levels, this endpoint will be evaluated in each arm about one month after the booster (2nd) vaccination is administered. In Arm A, this will be evaluated at the beginning of cycle 6. In Arm B, this corresponds to the beginning of cycle 4. Secondary aims will include response, progression free survival, and immunologic response to primary tumor cells.

Lenalidomide treatment will be administered on a continuous basis. For the sake of convenience of dose-modification and response and toxicity monitoring, one cycle will be defined as 28 days. Treatment will be administered at 2.5 mg/day during the first cycle to minimize risk for tumor flare and/or tumor lysis. If tolerated, the dose will be increased to 5 mg/day beginning in the second cycle. Treatment will continue for at least 24 cycles (approximately 2 years) in the absence of disease progression or irreversible Grade  $\geq$  3 hematologic or non-hematologic toxicities.

Patients will receive 2 doses of 13-valent protein-conjugated pneumococcal vaccine (Prevnar 13, PCV13) administered 2 months apart. In Arm A, the vaccine will be administered at the beginning of Cycles 3 and 5. In Arm B, the vaccine will be administered at the beginning of Cycles 1 and 3.

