### 5.1.1 Lenalidomide

Lenalidomide treatment will be administered on a continuous basis. However, for convenience of dose-modification, response, and toxicity monitoring, the treatment period will be divided into cycles of 28-day length. Lenalidomide will be dispensed in no more than one 28-day supply. Before each supply is released, each patient's medication calendar from the previous cycle will be reviewed to assess compliance. Patients will also be required to review the Lenalidomide Information Sheet ([Appendix E](#)) and the Education and Counseling Guidance Documents ([Appendix D](#)) prior to receiving each monthly supply of lenalidomide.

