### 5.3 Duration of Therapy

Patients demonstrating clinical benefit, defined as achievement of an objective response (CR, CRi, or PR) or stable disease (SD), may continue therapy for up to 24 cycles (approximately 2 years) of treatment with lenalidomide. Therapy beyond 24 cycles may be considered after discussion with the principal investigator and consultation with the study sponsor.

Investigators are encouraged to keep patients experiencing clinical benefit on study unless significant toxicity puts the subject at risk or routine noncompliance puts the study outcomes at risk. If the subject meets any 1 of the following criteria, withdrawal from treatment is mandatory:

- Disease progression meeting 2008 IWCLL consensus criteria for treatment.
- Intercurrent illness that prevents further lenalidomide administration.
- Any treatment-related Grade 4 non-hematologic toxicity.
- Unacceptable and/or unmanageable Grade  $\geq 3$  toxicity attributable to lenalidomide.
- Any treatment-related hematologic or non-hematologic toxicity delaying treatment more than 14 days.

- Development of autoimmune hemolytic anemia (AIHA) or immune-mediated thrombocytopenia (ITP)
- Subject elects to withdraw from study or becomes pregnant.
- General or specific changes in the patient's condition rendering the patient unacceptable for further treatment in the judgment of the investigator.
- Subject is noncompliant with study procedures and/or scheduled evaluations.
- Investigator considers withdrawal to be in the best interest of the subject.
- Diagnosis of new or secondary malignancies after initiating treatment

Subjects with inadequate study drug compliance (i.e.  $\leq$  80% of planned doses administered) may be replaced.

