- i. Risk stratification studies will include serum  $\beta$ 2-microglobulin in addition to tests performed on the screening bone marrow biopsy specimen: IgVH mutational analysis (unless already known), interphase cytogenetics, stimulated karyotype and standard CLL FISH panel.
- j. Allopurinol should be administered beginning 3 days before first lenalidomide administration and continued through the first cycle of lenalidomide treatment in its entirety. Allopurinol can be continued during subsequent cycles at the treating physician's discretion.
- k. Thromboprophylaxis should begin with lenalidomide in patients at high-risk for venous or arterial thromboembolism (see [5.2.3](#)).
- l. Only enough lenalidomide for 28 days or one cycle of study treatment (whichever is shorter) may be provided to the patient each cycle.
- m. CBC is checked on D1 and D8 during the first cycle of lenalidomide exposure and during the second cycle and/or any subsequent cycle in which the dose of lenalidomide has been escalated. CBC should be checked weekly during any subsequent cycle in which the dose of lenalidomide has been reduced for hematologic toxicity.
- n. Response is assessed clinically (CBC, physical examination) after every 2 cycles of lenalidomide treatment beginning with Cycle 3 (Arm A) or Cycle 5 (Arm B), respectively. For patients meeting clinical criteria for CR for  $\geq$  2 months, bone marrow biopsy and CT scans should be performed to confirm response.
- o. The End of Therapy visit is defined as that occurring after 24 cycles. Patients discontinuing treatment at other times secondary to toxicity, progression, or preference only need the clinical assessment (except informed consent and education and counseling) and a complete blood count. Patients discontinuing for any reason are followed for at least 30 days to ensure resolution of any adverse events; however, these patients will still be followed for outcome until meeting criteria outlined in footnote "p" below.
- p. Patients no longer receiving active treatment are followed every 3 months during the first year and every 6 months thereafter until the patient receives a new CLL therapy, withdrawal of consent, or death.
- q. Unless completed within the last month.
- r. CT scans of the chest, abdomen, and pelvis.

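### Time to treatment failure counts every discontinuation as an event, so patients who stop on completing the planned 24 cycles are scored as failures if the rule is applied as written

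*Combined protocol and SAP*

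**What the plan says.** The tolerability paragraph of Section 13.5 lists time to treatment failure, "defined as the time from study entry to discontinuation of treatment", and adds that "we will also summarize reasons patients discontinue study treatment". Nothing there or elsewhere says how a patient who finishes planned therapy is handled.

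Planned length of treatment is described in three places:

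- Section 5.3: patients with clinical benefit "may continue therapy for up to 24 cycles (approximately 2 years) of treatment with lenalidomide". It adds that "Therapy beyond 24 cycles may be considered after discussion with the principal investigator", with sponsor consultation.
- Schema, Treatment Plan: "Treatment will continue for at least 24 cycles (approximately 2 years) in the absence of disease progression" or irreversible severe toxicity.
- Study Calendar, footnote o: "The End of Therapy visit is defined as that occurring after 24 cycles". The footnote then sets lighter requirements for those who stop at any other time because of toxicity, progression or choice. That wording treats the 24-cycle stop as one more discontinuation.

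Under Section 5.1.1 and Table 2, Arm A starts lenalidomide in Cycle 1. Arm B has vaccine only in Cycles 1 to 3 and starts lenalidomide in Cycle 4. Section 13.5 says time-to-event outcomes will be explored between arms with Kaplan-Meier methods, without formal comparison.

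**The concern.** A failure endpoint should separate patients whose treatment broke down from those who finished it. This one does not. A patient who takes all planned lenalidomide, is in response and stops on schedule has the same event as one withdrawn for toxicity. Any Kaplan-Meier curve then drops at the planned end of therapy by the fraction who stop there, and that drop says nothing about tolerability.

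The second problem is the time origin. Both clocks start at study entry, but an Arm B patient cannot have a lenalidomide-related stop during the first three cycles. Curves compared between arms therefore include a schedule difference. Related parts of the plan use other origins: toxicity is evaluable from first lenalidomide (Section 13.6.1), and progression-free survival runs from start of treatment (Section 11.7).

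At stake is how one secondary tolerability summary is read. The primary antibody endpoint, the sample size and the complete-response rule do not depend on it.

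**Working it through.** The plan gives no expected value, event count or power for this outcome, so there is no figure to reproduce.

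**Inputs from the plan.** Cycle length is 28 days (Section 5.1.1: "the treatment period will be divided into cycles of 28-day length"). Planned therapy is 24 cycles (Section 5.3). Lenalidomide starts in Cycle 1 in Arm A and Cycle 4 in Arm B (Table 2).

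**Step 1: cycle arithmetic.**

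- Arm B lead-in without lenalidomide: 3 × 28 = 84 days.
- Arm A completer: 24 × 28 = 672 days from the start of Cycle 1.
- Arm B completer, counting 24 lenalidomide cycles (the natural reading of Section 5.3): 84 + 672 = 756 days.
- Arm B completer, counting 24 protocol cycles from Cycle 1 (a possible reading of footnote o): 672 days, the same as Arm A.

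Under the second reading, completion falls on the same day in both arms, but the 84-day lead-in still precedes any lenalidomide-related stop in Arm B patients who reach Cycle 4.

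**Step 2: how many completers would be scored as failures.** The documents give no completion rate, so this is an illustration. Assume an exponential time to unplanned stopping of lenalidomide with median m, the same hazard in both arms, 24 lenalidomide cycles planned, and that every completer stops. The completer share is exp(−ln 2 × 672 / m), with one month = 30.4375 days.

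Assuming also no Arm B events in the lead-in, the median time to treatment failure is min(m, 672) in Arm A and 84 days more in Arm B.

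| Assumed median on lenalidomide | m (days) | Completers scored as failures | Median, A v B (days) |
|---|---|---|---|
| 12 months | 365.25 | 28% | 365 v 449 |
| 24 months | 730.5 | 53% | 672 v 756 |
| 36 months | 1,095.75 | 65% | 672 v 756 |

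**Step 3: size of the artefact between arms.** A simulation under the same assumptions (4,000 per arm) gave these Cox hazard ratios, B to A, although the true hazards on lenalidomide are identical. The plan fits no such model; the ratios only measure how far apart the curves would lie.

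| Rule | 12 months | 24 months | 36 months |
|---|---|---|---|
| As written: completion is an event, clock from study entry | 0.56 | 0.41 | 0.29 |
| Completion censored, clock from study entry | 0.79 | 0.87 | 0.84 |
| Completion censored, clock from first lenalidomide | 0.97 | 1.04 | 0.98 |

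Censoring completers removes most of the distortion. The remainder comes from the lead-in.

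**Step 4: sensitivity to the lead-in assumption.** If Arm B patients leave at the same hazard from study entry onward, Arm B's mean gain shrinks to 22, 43 and 53 days for the three medians. At 12 months the arm medians are then equal at 365 days. The 84-day figure is therefore the offset for Arm B patients who reach Cycle 4, not an average gain over everyone randomized.

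**The case against.** The strongest reply is that little depends on this outcome. It is not among the objectives in Section 1 and has no hypothesis or decision rule. Section 13.5 rules out formal between-arm comparison of time-to-event outcomes. Reasons for stopping are summarized alongside it, and Section 5.5 requires the removal date and reason on the case report form, so completers can be identified at analysis. This stands as a limit on importance. It does not repair the estimate: a table of reasons leaves the events in the curve unchanged, and the curves are to be explored between arms.

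It can also be said that no sentence calls a completer a failure, and that Section 13.6.2 reserves treatment failure for response categories 4 to 9, which exclude complete response, partial response and stable disease. That rule serves the response analysis. Beside the definition in Section 13.5 it gives the term two meanings, and the event in Section 13.5 remains unrestricted.

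The study-entry clock is defensible. It keeps all randomized patients and follows the whole regimen, which in Arm B begins with vaccine. A clock from first lenalidomide conditions on a post-randomization event and loses Arm B patients who leave in Cycles 1 to 3. This objection stands, and it is why study entry should remain the main clock.

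Two stronger readings are tempting. A reader might infer that the curve must fall to near zero at the end of planned therapy. The documents do not support this: Section 5.3 permits longer treatment, the Schema makes 24 cycles a minimum, and Section 9 of the 2024 version still mentions a small number of patients on treatment. A reader might also infer that the medians are fixed by the schedule at 672 v 756 days. That requires at least half of each arm to reach 24 cycles and then stop, and lenalidomide cycles to be the unit counted. The first is unknown: with a 12-month median on drug, only 28% complete. The second is not settled by the documents.

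**Conclusion.** The definition, applied as written, scores patients who stop on completing planned therapy as treatment failures. That follows from an unrestricted event, the absence of a censoring rule, and footnote o's treatment of the 24-cycle stop as a discontinuation.

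How many patients are affected cannot be determined from the documents. The range of 28% to 65% rests on an assumed exponential median of 12 to 36 months on lenalidomide and on every completer stopping; patients who continue by agreement lower it.

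The 84-day lead-in is exact for Arm B patients who reach Cycle 4. Whether completion itself falls 84 days apart (672 v 756) or on the same day (672 in both arms) depends on which cycles are counted. The consequence is limited to a descriptive tolerability outcome, but the correction is simple enough that it should be made.

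**What to change.** In Section 13.5, define the event as discontinuation for progression, toxicity, death, withdrawal or another unplanned cause, and censor at protocol-defined completion of therapy. State also how patients who continue beyond completion by agreement are handled.

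Keep study entry as the main clock so that all randomized patients are included. Add a supplementary display timed from first lenalidomide dose, with a note that it leaves out Arm B patients who drop out in Cycles 1 to 3.

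The Schema, Section 5.3 and Study Calendar footnote o must be reconciled on planned treatment length, including whether Arm B's count runs from Cycle 1 or from first lenalidomide. Otherwise completion, and so the censoring date, is ambiguous.

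The analysis change costs a sentence or two and one extra figure. Stop dates and reasons are already required under Section 5.5, so no new data are needed.
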